Histopathological Evaluation of the Periodontal Ligament and Cementum of Extracted Teeth Subjected to Laser Ablation with Indocyanine Green

Device Investigated: Leonardo Diode Laser with the LEAP Laser Absorption Solution

Indication Studied: Pulpectomy. Specifically, a laser ablation step facilitated with the LEAP solution, added to the standard procedure for tooth pulpectomy, does not present a risk of damage to tissues and structures external of the treated root as a consequence of possible temperature increases.

Sponsor: CAO Group, Inc.

Protocol ID: 70009423.2.0000.5539

Development Phase: Performance Validation

NCT ID: Not Yet Assigned

Anticipated Initiation Date: 1 August 2023

Anticipated Completion Date: 30 September 2023

Document Date: 10 July 2023

DATA COLLECTION INSTRUMENT

Clinical Procedures and Sample Collection

Study design and population

The patients will be treated at the Unicesumar Dental Clinic. Ten healthy female and male patients, over 18 years old, and in need of tooth extraction, will be selected for the study. Patient selection will be carried out through anamnesis and clinical/imaginological examinations. The inclusion criterion are: lower incisors with indication for extraction.

The exclusion criteria are: other dental groups; teeth that have periodontal disease beyond the apical third of the root; and teeth that do not require tooth extraction.

At least ten teeth will be included in this study for the treatment group, and two other teeth will be used as a control group. The study is porposed under submission to the Human Research Ethics Committee (CAAE 70009423.2.0000.5539) and all patients who agreed to participate in the research will sign the Informed Consent Form.

Endodontic treatment procedure

Patients will be anesthetized with 3% Mepivacaine with 1:100,000 epinephrine (Mepiadre, DFL, RJ, Brazil), and the teeth will be isolated with a rubber dam (Madeitex, São José dos Campos, Brazil). The operative field will then be disinfected with a povidone-iodine solution. After coronary accesses, the root canals will be prepared to #35/0.04 reciprocating instrument (Blue S-one, Fanta Dental, Shanghai, China). All root canals will receive irrigation with 2.5% sodium hypochlorite, with a syringe (Descarpack, São Paulo, Brazil) and irrigation needle (Navitip, Ultradent, Utah, USA). At the end of preparation, each canal will receive the following final irrigation protocol: 10 ml of sodium hypochlorite, with 30-second activation (PUI) with an E1 ultrasonic insert (Helse, Santa Rosa do Viterbo, SP, Brazil), coupled to an ultrasound device (PM 200, EMS, Switzerland) at 10% power. Second activation with 10 ml of EDTA-T (Fórmula &

Ação, São Paulo, Brazil) for 30 seconds with the same parameters. Third activation with 10 ml of sodium hypochlorite for 30 seconds with the same parameters.

There will be no questionnaire.

Laser Ablation Protocol

After chemo-mechanical preparation, all root canals of all patients assigned to the trial intevention will receive laser ablation (LA) therapy with the indocyanine green solution (ICG). First, the root canals will be filled with 0.05% ICG solution (MP Biomedicals - Thermo Fisher Scientific, Pittsburgh, PA) which will remain in the root canal for 1 minute (pre-irradiation time). After this period, a #20 laser fiber will be inserted into the root canals to the working length. Then, 810 nm wavelength infrared diode laser (Leonardo, CAO Group, West Jordan-UT) will be activated with a power of 2.5 W, an emission interval of 300 milliseconds, and a pulse duration of 100 milliseconds. After activation commences, circular movements will be performed for 30 seconds together with the movement of removing the laser fiber. After the first activation, there will be a 30-second pause and a new 30-second activation cycle will be performed in the same way as the previous one. At the end of LA therapy with ICG, the root canals will be irrigated with 5 ml of saline solution and dried with absorbent paper cones (Dentsply Maillefer, Ballaigues, Switzerland).

Tooth extraction and histotechnical processing

After the previous procedure, an incision will be made in the gingival tissue around the tooth to be extracted, which will be gently moved away to expose the tooth neck. Then, with an atraumatic extraction kit, the dental element will be dislocated and, using forceps and/or an extractor, the element will be removed. Finally, a suture will be placed to bring the edges of the gingival tissue around the socket as close as possible.

From the dental element, the apical part of the element will be obtained together with the periodontal ligament, which will be immediately placed in individual bottles duly identified, containing 10% formalin solution, buffered with neutral pH, and stored for the first 20 hours and then washed in running water for another 12 hours to remove the fixing solution. After fixation, the pieces will be demineralized in a 10% EDTA solution28. Then, the pieces will be washed in running water, dehydrated in alcohol, cleared in xylene and embedded in paraffin. After inclusion, the pieces will be cut with semi-serial cuts, 3 µm thick, carried out using a microtome (Leica - RM 2045). For each specimen, 5 slides with 3 tissue sections will be prepared and stained with Hematoxylin-Eosin and Picrosirius red29.

Analysis of histological results

Analyzes will be performed at 400x magnification under light microscopy (DM 4000 B, Leica, Wetzlar, Germany) by a single, calibrated, and blinded operator. Histological analysis will be used to characterize the morphological structures of the periodontal ligament with the aim of identifying possible pathological changes. The results will be presented through descriptive and qualitative analysis. The analysis will consider: inflammatory infiltrate in terms of its intensity and extent; periodontal ligament organization; collagen fibers maturation; inflammatory and/or replacement resorption; and dental ankylosis. The two teeth used as controls will serve as baseline parameters to analyze possible morphological changes.

The inflammatory reaction will be scored according to the average number of inflammatory cells present in the middle third of the root of the teeth, being: Score 0, no or few cells (normal); Score 1, <25 cells (mild); Score 2, 25-125 cells (moderate); Score 3, >125 cells (severe).

For the periodontal ligament organization analysis, the percentage of organization will be considered, where: Score 0, total organization (100%), Score 1, organization greater than 75% and less than 100%; Score 2, greater than 50% and less than 75%; and Score 3, organization of less than 50%.

Inflammatory and/or replacement resorption and dental ankylosis will be considered according to their intensity and extent, where: Score 0, absent, without the presence of the mentioned events; Score 1, change in an area less than 25%; Score 2, change in an area greater than 25% and less than 50%; Score 3, change in an area greater than 50%.

Statistical Analysis Plan

All statistical analysis will be performed using SigmaPlot 12.0[™] software (Chicago, IL, USA). The data obtained will be submitted to the Shapiro-Wilk normality test. Then, for comparisons between the Control and Treatment group, the Mann-Whitney U test will be used for nonparametric data. For parametric data, the Student t-test will be used. The level of significance will be set at 5%.

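### The safety claim covers every tissue outside the root, but the plan examines only part of the extracted root and its adhering ligament

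*Combined protocol and SAP*

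**What the plan says.** The claim is in the Indication Studied line at the head of the protocol: the added laser step "does not present a risk of damage to tissues and structures external of the treated root as a consequence of possible temperature increases".

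The title describes a smaller study: "Histopathological Evaluation of the Periodontal Ligament and Cementum of Extracted Teeth".

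Under Tooth extraction and histotechnical processing, "the dental element will be dislocated and, using forceps and/or an extractor, the element will be removed". From the removed tooth, "the apical part of the element will be obtained together with the periodontal ligament", and that piece goes to histology. The socket is mentioned only at closure: "a suture will be placed to bring the edges of the gingival tissue around the socket as close as possible".

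Under Analysis of histological results, the aim is again limited to ligament: "Histological analysis will be used to characterize the morphological structures of the periodontal ligament". The outcomes are inflammatory infiltrate, ligament organisation, collagen maturation, and "inflammatory and/or replacement resorption; and dental ankylosis". Inflammation is scored from cell counts in the middle third of the root. Ligament organisation is scored 0 to 3 by percentage bands, with no statement of what the percentage is taken over.

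**The concern.** The claim has no boundary outside the root. Alveolar bone lies within it, and so does the ligament along the whole root, including any that tears and stays in the socket. The plan looks at neither the bone nor the retained ligament. If the result is favourable and reported in the words of the indication, readers will take it as evidence about tissue that was never examined.

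A smaller issue follows from the same extraction step. Removing a tooth parts the ligament, so some root surface on the sections may be bare. The organisation score does not say whether bare surface counts as disorganised or is left out. The reader of the slides would have to decide, and that decision can change the score.

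**Working it through.** **Scope.** The plan states no figure that bears on this, so the check sets the texts side by side.

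| Element | Where | Tissue covered |
|---|---|---|
| Claim | Indication Studied | Anything outside the treated root; no limit given |
| Title | Head of protocol | Ligament and cementum of extracted teeth |
| Specimen kept | Tooth extraction and histotechnical processing | Apical part of the tooth with its ligament |
| Histological aim | Analysis of histological results | Ligament |
| Inflammation score | Same section | Middle third of the root |
| Resorption, ankylosis | Same section | Extracted piece |
| Socket | Tooth extraction and histotechnical processing | Gingiva sutured; nothing assessed |

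1. Socket bone is in the first row and in no later one. The documents describe no bone sampling, no imaging after treatment, no temperature measurement and no follow-up after extraction.
2. Resorption and ankylosis concern the root and its interface with bone, but they are scored on the extracted piece. A bone fragment that happened to come away would not be a planned sample.
3. Ligament left in the socket is not recovered, so no score includes it.
4. The examined portion is itself unsettled: the apical part is retained, yet inflammation is scored in the middle third.

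More teeth would not change any of these four lines.

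**Organisation score.** Bands from the protocol: 0 for 100%; 1 for above 75% and below 100%; 2 for above 50% and below 75%; 3 for below 50%. Let b be the bare share of root surface. The documents give no value for b, so the values below are assumptions, and the ligament that remains is taken as fully organised.

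- Bare surface left out: (1 − b)/(1 − b) = 100%, Score 0, whatever b is.
- Bare surface counted as disorganised: (1 − b)/1.

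| b (assumed) | Bare left out | Bare counted |
|---|---|---|
| 10% | 100%, Score 0 | 90%, Score 1 |
| 20% | 100%, Score 0 | 80%, Score 1 |
| 40% | 100%, Score 0 | 60%, Score 2 |
| 60% | 100%, Score 0 | 40%, Score 3 |

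**What a separate bare-surface measure could show.** Study design and population gives at least ten treated teeth and two controls. Taking exactly 10 and 2, there are C(12,2) = 66 possible allocations. For an exact two-sided Mann-Whitney test without ties (the plan does not state sidedness), complete separation gives p = 2/66 = 0.030 and the next value is 4/66 = 0.061. Anything short of complete separation misses the 5% level, so such a measure can only be descriptive.

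**The case against.** The strongest defence is that the study is already limited where it counts. The title and the histological aim both confine it to ligament (the title adds cementum), and the broad phrase stands only in the header. The indication does not contain the word all. This is largely right, and it makes the repair a matter of wording. It does not remove the mismatch, because the header is where the claim is stated.

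A second defence is that the heat source sits in the canal and the ligament lies between root and bone, so intact ligament suggests bone that was not overheated. That is a reasonable inference, and not taking bone from patients is a defensible choice. But the protocol neither states the argument nor tests it, no temperature is recorded, and the argument says nothing about ligament that was not recovered.

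On the score, the protocol specifies an extraction kit described as atraumatic, a calibrated and blinded reader, and control teeth as a baseline. Blinding does prevent a choice about bare root that knowingly depends on group, and the controls give some reference for tearing. Neither replaces a written rule.

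A reader might go further and infer that the comparison is biased towards no damage, because heated ligament would detach more easily and drop out of the treated group's scores. The documents offer nothing to support that; it is a hypothesis. A reader might also take the two-grade difference at 40% bare root as the size of the problem. It is not: the difference is set by the assumed input and runs from one grade to three over the range shown.

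**Conclusion.** The main point holds. As written, a favourable result could not support the indication at its stated scope, because socket bone and retained ligament are examined in no tooth and the hard-tissue outcomes are read only on the extracted piece. This rests on the text alone and needs no numerical assumption. It does not make the study uninformative: it can still describe the cementum and ligament recovered on the root portion that is examined.

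The scoring point is secondary and conditional. The missing denominator is a fact of the text. How much it matters depends on how much root is bare, which the documents do not say, and the table assumes that the remaining ligament is fully organised. It shows that a rule is needed, not that the results would be wrong by a known amount or in a known direction.

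**What to change.** 1. Reconcile the examined portion first. The specimen section keeps the apical part and the inflammation score uses the middle third; both should name the same portion of root.
2. Then restate the claim in Indication Studied along these lines: *no histological damage seen in the cementum and adhering periodontal ligament of the examined root portion of extracted lower incisors*. Remove the wider reference to tissues outside the root. Keeping it would require an added assessment of those tissues, which the plan does not contain.
3. In the organisation score, state that the percentage is taken over the ligament present on the section.
4. Because that rule by itself would hide detachment, record the percentage of root surface without ligament on the same sections, read blinded, and report it by group as a descriptive measure with no significance test relied on.

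The cost is a narrower claim, some rewording, and one extra reading on sections already planned. No added patients or procedures are needed.

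### The tooth criteria admit existing root resorption, ankylosis and periapical lesions, so some findings scored after the laser step may have been there before it

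*Combined protocol and SAP*

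**What the plan says.** Under *Study design and population*, the combined protocol and SAP gives one inclusion rule: "The inclusion criterion are: lower incisors with indication for extraction". The exclusions are three: "The exclusion criteria are: other dental groups; teeth that have periodontal disease beyond the apical third of the root; and teeth that do not require" extraction. At patient level it adds "Ten healthy female and male patients, over 18 years old, and in need of tooth extraction, will be selected for the study". On screening it says "Patient selection will be carried out through anamnesis and clinical/imaginological examinations", but it names no imaging finding that would disqualify a tooth. The groups are set as follows: "At least ten teeth will be included in this study for the treatment group, and two other teeth will be used as a control group".

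Under *Analysis of histological results*, the features assessed include inflammatory infiltrate, ligament organization, and "inflammatory and/or replacement resorption; and dental ankylosis". For resorption and ankylosis the lowest grade is "Score 0, absent, without the presence of the mentioned events" and the next is "Score 1, change in an area less than 25" per cent, with higher grades for larger areas. The two control teeth are named as the baseline. Inflammation is scored on cell counts in the middle third of the root; the organization, resorption and ankylosis scores carry no such restriction.

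Under *Tooth extraction and histotechnical processing*, the specimen is the apical portion with its ligament, and extraction is the next step after the laser.

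**The concern.** A tooth can need extraction because of the very conditions that the study grades. A lower incisor with resorption, ankylosis or an apical lesion is eligible as written, and it may have no periodontal disease at all, so the periodontal exclusion need not catch it. The word healthy describes the patient and not the tooth.

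The scores record what is on the slide. No rule separates old from new change, and no pre-treatment finding on the same tooth enters the scoring. Attribution to the laser therefore rests wholly on the contrast with two control teeth drawn under the same open criteria, and no random or matched assignment is described.

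The study sets out to show that the added laser step does not harm tissue outside the root. Prior disease in a treated tooth works against that claim by imitating harm. Prior disease in a control works in its favour by raising the reference. The second error matters more for a safety conclusion.

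**Working it through.** The plan gives no figure on this point to reproduce: no prevalence, no effect size and no sample-size derivation. The check has two parts.

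**1. Criteria set against outcomes**

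| Condition at entry | Excluded? | Scored afterwards? |
|---|---|---|
| Root resorption | No | Yes, by area |
| Ankylosis | No | Yes, by area |
| Periapical lesion | No | Not by name; may affect ligament organization in the apical specimen |
| Previous root filling | No | No |

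The first three rows are the gap. On timing, no interval is stated between laser and extraction. Resorption or ankylosis on the slide is therefore more plausibly old than new, yet it is scored and compared as an outcome.

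**2. Illustration of size**

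Inputs: ten treated and two control teeth, from *Study design and population*; prevalence *q* of a pre-existing scored finding, assumed at 0.10 to 0.30 because the documents give none. Teeth are treated as independent. This is approximate, because twelve teeth from ten patients would mean that some share a mouth.

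- Treated teeth affected, on average: 10*q* = 10 × 0.10 = 1, and 10 × 0.30 = 3. This is an upper figure for the number scoring above 0, because it needs every affected tooth to register on the scale.
- At least one of two controls affected: 1 − (1 − *q*)² = 1 − 0.90² = 0.19, and 1 − 0.70² = 0.51.
- At least one treated tooth affected while both controls are clean: [1 − (1 − *q*)¹⁰] × (1 − *q*)².
  - *q* = 0.10: 0.651 × 0.81 = 0.53
  - *q* = 0.20: 0.893 × 0.64 = 0.57
  - *q* = 0.30: 0.972 × 0.49 = 0.48

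Over this range there is roughly an even chance of a pattern that resembles laser damage without any laser effect. Two controls do not protect against it.

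**The case against.** Several points on the other side have force.

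- **Inflammation.** The cell count is taken in the middle third of the root, so a purely apical lesion need not change it. This stands. A reader might infer that apical infiltrate feeds directly into the inflammation score; the scoring rule does not support that.
- **Root filling.** A reader might list a previous root filling among the contaminated outcomes. It is not scored. The stated indication is pulpectomy, and *Endodontic treatment procedure* goes from access to preparation with no step for removing an old filling, so unfilled canals seem to be presupposed. A filled tooth is a mismatch with the indication and not a demonstrated source of bias in the scores.
- **Comparator.** The scale grades presence and extent, and attribution is meant to come from the controls. That is true, but the comparison works only if prior disease is balanced between groups, and nothing in the plan secures that with two controls.
- **Timing.** Removing prior cases does not show that resorption or ankylosis can register a laser effect in the time available. This stands. The change removes misleading positives; it does not make these scores sensitive.
- **Size.** The 10–30% is assumed, and not every affected tooth must score above 0. The figures are illustrations. The gap in the criteria does not depend on them.

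**Conclusion.** The concern holds for resorption, ankylosis and ligament organization. In any tooth that enters with one of these conditions, or with an apical lesion, the plan cannot separate prior disease from a laser effect. The inflammation score is less exposed.

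A reader might go further and conclude that the trial cannot say whether the laser damages external tissue. The documents do not support that: if the treated teeth all scored 0, prior disease would have obscured nothing in them and the result would still be informative. The ambiguity is confined to affected teeth and to comparisons that use an affected control.

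On the assumed 10–30% prevalence, with independent teeth, the chance of at least one affected control is 19–51%, and up to 1–3 of ten treated teeth could score above 0 without any laser effect. This is worth correcting before enrolment because the remedy is cheap.

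**What to change.** Add one tooth exclusion under *Study design and population*, applied to treated and control teeth alike and before assignment: *radiographic root resorption, ankylosis or periapical radiolucency on the screening image*. Also record, for every tooth, the reason for extraction and the imaging status at screening, and present the histological scores alongside them. Previous root filling may be added to the exclusions, on the separate ground that it does not fit the pulpectomy indication.

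Imaging is already part of patient selection, so no new procedure should be needed, provided that the unspecified imaging examination shows the root apex adequately. The cost is extra screening in a window planned from 1 August to 30 September 2023. At the assumed prevalences, twelve eligible teeth would need about 12 / 0.90 = 13 to 12 / 0.70 = 17 candidates, and more if these conditions are commoner among teeth due for extraction. If recruitment cannot bear that, recording status and reporting scores by it is a weaker fallback. Imaging will miss small lesions, so the problem is reduced and not removed.

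### The two control teeth are the only reference for laser damage, yet the plan gives no rule for choosing them and does not randomise

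*Combined protocol and SAP*

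**What the plan says.** On numbers, the section Study design and population states "Ten healthy female and male patients, over 18 years old, and in need of tooth extraction, will be selected for the study", then "At least ten teeth will be included in this study for the treatment group", and adds that "two other teeth will be used as a control group". That makes at least twelve teeth for ten patients. The source of the two controls is not given.

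On eligibility, the same section admits "lower incisors with indication for extraction" and excludes "teeth that have periodontal disease beyond the apical third of the root". Periodontal disease short of that limit is therefore allowed. Selection uses history, clinical examination and imaging.

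On allocation, the only wording is in Laser Ablation Protocol: "all root canals of all patients assigned to the trial intevention will receive laser ablation (LA) therapy". This speaks of assigned patients, whereas the group sizes are counted in teeth. Who assigns, when and by what method is not stated, and randomisation is not mentioned anywhere.

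On the use of the controls, Analysis of histological results says: "The two teeth used as controls will serve as baseline parameters to analyze possible morphological changes". The slides are read "by a single, calibrated, and blinded operator". The Statistical Analysis Plan then compares control with treatment by Mann-Whitney or t-test at the 5% level.

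**The concern.** The outcomes are inflammation, ligament organisation, resorption and ankylosis. Disease present before treatment can affect these, so two eligible teeth may score differently with no laser involved. Tissue is obtained only by extraction, so a treated tooth cannot have its own pre-treatment histology. That is inherent in the design and not an omission, but it leaves the two controls as the only means of separating earlier disease from laser damage.

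Because tooth condition is known from screening, any non-random choice of controls may be related to it. If the more diseased teeth become controls, the reference is raised and real damage is hidden. If the healthiest become controls, damage may appear where there is none. The first direction matters more here, because the stated indication is that the added laser step does not endanger tissue outside the root. A blinded reader protects the scoring and cannot correct which teeth were put in which group.

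**Working it through.** The plan gives no effect size, SD or power, so it has no figure to reproduce.

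**Inputs from the plan:** 10 treated and 2 control teeth (the stated minimum), scores 0 to 3, Mann-Whitney test, 5% level. Sidedness is not stated; two-sided is assumed.

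**Assumed for illustration:** 4 of 12 teeth start at score 2 and 8 at score 0, and the laser adds exactly 1 to each treated tooth.

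**Step 1. What the plan's test can see.** There are C(12,2) = 66 ways to pick two controls. Without ties, complete separation gives two-sided p = 2/66 = 0.030; the next result gives 4/66 = 0.061. Significance thus requires both controls to lie beyond all ten treated teeth.

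**Step 2. Same harm, different controls.** The p-value is the share of the 66 splits whose control rank sum lies at least as far from its expectation, 2 × 13/2 = 13, as the observed one.

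| Diseased controls | Treated mean | Control mean | Difference | Control rank sum | Exact p |
|---|---|---|---|---|---|
| 0 | (4×3 + 6×1)/10 = 1.8 | 0 | +1.8 | 1.5 + 1.5 = 3 | 1/66 = 0.015 |
| 1 | (3×3 + 7×1)/10 = 1.6 | 1 | +0.6 | 1 + 9 = 10 | 56/66 = 0.85 |
| 2 | (2×3 + 8×1)/10 = 1.4 | 2 | -0.6 | 9.5 + 9.5 = 19 | 6/66 = 0.09 |

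The first p is below 0.030 because, with ties, the opposite extreme has rank sum 21, only 8 from 13, against 10 for the observed split.

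**Step 3. What a random draw does.** The chances of 0, 1 and 2 diseased controls are 28/66 = 42%, 32/66 = 48% and 6/66 = 9%. The expected difference is (28×1.8 + 32×0.6 - 6×0.6)/66 = 66/66 = 1.0, exactly the assumed effect, so the draw is unbiased. The harm is significant only in the first case, so it is missed in (32 + 6)/66 = 58% of draws.

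**Step 4. Range over the unknown number of diseased teeth**, under a random draw:

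| Diseased of 12 | No diseased control | One | Two |
|---|---|---|---|
| 2 | 68% | 30% | 1.5% |
| 4 | 42% | 48% | 9% |
| 6 | 23% | 55% | 23% |
| 8 | 9% | 48% | 42% |

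**Step 5. Check without the illustrative scores.** Normal scores were simulated, 100,000 trials per setting. Visible disease correlates with the histology score at an assumed rho, and the controls are the two least or two most diseased teeth.

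| rho | No effect, least diseased chosen: false harm | True 2 SD harm, most diseased chosen: power |
|---|---|---|
| 0.3 | 5% | 29% |
| 0.5 | 10% | 20% |
| 0.7 | 20% | 12% |
| 1.0 | 100% | 4% |
| Random draw | 1.5% | 47% |

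The bias in the false-harm column runs from about 0.5 SD (rho 0.3) to 1.6 SD (rho 1.0). Under a random draw it is 0, but the standard error of the difference is still sqrt(1/10 + 1/2) = 0.77 SD.

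**The case against.** The strongest reply is that the illustration mainly shows that two controls are too few, which randomisation leaves unchanged. This stands in part. A reader might infer that a random draw removes the problem, or that the 9% chance of two diseased controls is all the risk that remains. Neither follows: the 48% chance of one diseased control also matters, and the assumed harm is missed in 58% of fair draws. What the draw removes is systematic selection.

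Other tempting readings also go too far:

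- **That the treating clinician picks the controls, or that the choice is steered.** The document is silent on who assigns and how. Silence supports only that no method is stated.
- **That uniform harm would be shown as benefit.** The -0.6 has p = 0.09, which is no significant difference at the plan's 5% level. Harm is hidden, not reversed into a finding.
- **That disease at entry is common.** The patients are described as healthy, only lower incisors qualify, and some periodontal disease is excluded. Disease at entry is possible, but its frequency is unknown; the four in twelve is an assumption.
- **That the change costs nothing.** It adds no teeth only if all twelve come from one eligible pool and are handled alike up to the laser step. Endodontic treatment procedure is worded for all canals, which suggests common preparation, but it does not mention the controls.

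None of this supplies a rule for choosing the two controls.

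**Conclusion.** The concern holds as a matter of selection bias. The plan rests its comparison on two control teeth, states no way of choosing them, does not randomise, and admits teeth whose prior condition can affect the outcomes. The size of any bias depends on quantities that the plan does not give. In the assumed example the same harm yields a difference anywhere from +1.8 to -0.6; in the simulation, bias runs from about 0.5 to 1.6 SD as the assumed rho goes from 0.3 to 1.0. These figures show what a non-random choice could do, not what will happen.

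A concealed random draw brings the expected bias to zero and gives the exact test a valid basis. It leaves low precision: simulated power is about 14% for a 1 SD effect and 47% for 2 SD. A non-significant result would therefore remain weak evidence of safety. The change should be made.

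**What to change.** 1. State where the control teeth come from, and define a single pool of enrolled eligible teeth with its total fixed in advance.
2. Record each tooth's clinical and imaging status at screening, before allocation.
3. Draw the two controls from that pool with a computer-generated list, concealed from those who enrol and treat, before treatment starts. A rule that takes one control from every patient with two eligible incisors would not do, since it need not give exactly two controls and is not a draw of 2 from 12.
4. Reconcile the patient-level assignment wording in Laser Ablation Protocol with allocation by tooth.
5. Confirm that the two groups differ only in the laser step. If they do not, the comparison cannot isolate the laser however the teeth are drawn.
6. Tabulate screening status by group, and state in the report that chance imbalance with two controls remains.

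**Cost:** a short allocation list, someone to hold it, and a few protocol sentences. No teeth are added, provided one common pool exists. Reducing the chance imbalance itself would need more control teeth or stratification by recorded disease, which is a separate decision.
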